# Study Protocol

## Lay Summary (6th grade reading level):

Many people who abuse drugs also smoke cigarettes. Little is known about when in a person's drug treatment would be best to help them quit smoking. In this study, opioid dependent smokers will be asked to use a medication for 12 weeks. Each day, participants will respond to text messages related to quitting smoking. We will see participants once each month (4 visits) to ask about how ready they are to quit smoking. We plan to assess the feasibility of using this program in an opioid treatment clinic. We also plan to compare outcomes based on their clinic group.

**Purpose and Objectives:** Early evidence suggests that outcomes for substance use disorders (SUDs) may be improved for those who also smoke cigarettes, if smoking cessation is integrated with SUD treatment (Mannelli et al., 2013). Debate remains, however, over when to implement the smoking cessation treatment: immediately (to present a consistent treatment message) or after a delay (to allow patients to stabilize on their SUD pharmacotherapy). Thus, researchers have called for more work to determine whether the timing of treatment integration affects outcomes for both smoking and SUDs. At WVU, the Comprehensive Opioid Addiction Treatment (COAT) program provides access to a relatively large population of opioid-dependent smokers in various stages of SUD treatment: Days 1 to 90 (weekly group), Days 91 to 180 (biweekly group), and Days 181 to  $\geq 365$  (monthly group). In the proposed study, all three groups will receive varenicline pharmacotherapy and take varenicline per label instructions for 12 consecutive weeks. They will also provide a blood sample at one study visit for assessment of genetic markers for drug use. The goals of this work include:

**Primary Aims.** Demonstrate the feasibility of implementing smoking cessation treatment within an outpatient opioid-dependence treatment program via recruitment rates, adherence to treatment components, compliance with study requirements, and overall retention rates.

**Secondary Aims.** Compare COAT groups on outcomes related to drug use, including tobacco abstinence rates, days until successful cigarette abstinence, relapses for all drugs, withdrawal-related effects, and genetic markers for drug use.

Study results will shed light on the feasibility of implementing smoking cessation therapy within the COAT clinic, results that may generalize to other treatment programs for opioid dependence. Results will also provide initial evidence for whether smoking cessation timing affects abstinence outcomes for both tobacco and opioid use. Such data are directly relevant to communities within the state of West Virginia, which are disproportionately affected by the harms of these drugs. Among all states, WV ranks 50th for tobacco use prevalence, as well as 49th for deaths related to recreational use of opioids. Ultimately, this line of work may lead to recommendations for improving outcomes associated with opioid dependence treatment, as well as improving outcomes for a population of smokers that may otherwise not quit tobacco.

**Explain the Scientific Rationale:** Early evidence suggests that outcomes for substance use disorders (SUDs) may be improved for those who also smoke cigarettes, if smoking cessation is integrated with SUD treatment (Mannelli et al., 2013). For instance, among opioid-dependent smokers maintained on methadone (opioid pharmacotherapy) for up to 3 months, varenicline (tobacco pharmacotherapy) may promote an earlier successful cigarette quit day (de Dios et al., 2014) and improve long-term smoking abstinence rates (Nahvi et al., 2014), relative to placebo. Additionally, duration of smoking abstinence is associated positively with duration of opioid abstinence (Shoptaw et al., 2002), and changes in opioid pharmacotherapy dose are associated with changes in smoking behavior (Mello et al., 1985; Schmitz et al., 1994). Debate remains, however, over when to implement the smoking cessation treatment: immediately (to present a consistent treatment message) or after a delay (to allow patients to stabilize on their SUD pharmacotherapy). Thus, researchers have called for more work to determine whether the timing of treatment integration affects outcomes for both smoking and SUDs. At WVU, the Comprehensive Opioid Addiction Treatment (COAT) program provides access to a relatively large population of opioid-dependent smokers in various stages of SUD treatment: Days 1 to 90 (weekly group), Days 91 to 180 (biweekly group), and Days 181 to  $>365$  (monthly group). In the proposed study, all three groups will receive varenicline pharmacotherapy for 12 consecutive

weeks. Study results will shed light on the feasibility of implementing smoking cessation therapy within the COAT clinic, results that may generalize to other treatment programs for opioid dependence. Results will also provide initial evidence for whether smoking cessation timing affects abstinence outcomes for both tobacco and opioid use. Such data are directly relevant to communities within the state of West Virginia, which are disproportionately affected by the harms of these drugs. Among all states, WV ranks 50th for tobacco use prevalence, as well as 49th for deaths related to recreational use of opioids (CDC, 2013). Ultimately, this line of work may lead to recommendations for improving outcomes associated with opioid dependence treatment, as well as improving outcomes for a population of smokers that may otherwise not quit tobacco.

Probability of Group Assignment: Participants will be assigned to one of three groups based on duration of illicit-drug abstinence and time in COAT program. Groups will be assigned by the COAT program at the Chestnut Ridge Center and will be: 0 to 90 days abstinent (weekly group), 91 to 180 days abstinent (biweekly group), and 181 to  $\geq 365$  days abstinent (monthly group). All groups will receive the same varenicline treatment regimen per the label instructions.

Inclusion criteria: Participants must report smoking  $\geq 10$  cigarettes per day for  $\geq 1$  year. An expired air CO reading of  $\geq 10$  parts/million (ppm) at screening will verify current tobacco use status. Individuals must also indicate interest in making a quit attempt in the next 1-6 months (*Contemplation* or *Preparation* stages), as measured via the Stage of Change (SOC; DiClemente et al., 1991). The SOC categorizes smokers into one of five stages: 1) no plans to quit (*Precontemplation*) 2) plans to quit in the next 6 months (*Contemplation*), 3) plans to quit in the next 30 days, with a recent attempt made (*Preparation*), 4) currently trying to quit (*Action*), and 5) have already quit (*Maintenance*). Individuals in the *Precontemplation* stage are likely too disinterested in quitting to consider the cessation program offered during the intervention, while individuals in the *Action* stage may have already begun changing their smoking behavior. Importantly, 70-90% of smokers are considering quitting but are *not* actively trying to quit (i.e., are in contemplation or preparation; Velicer et al., 1995).

Exclusion criteria: Exclusion criteria include current engagement in any form of tobacco cessation (e.g., pharmacotherapy); current use of contraindicated medications (e.g., theophylline, warfarin, insulin, etc.); reports of smoking  $< 10$  cigarettes per day; expired air CO  $< 10$  ppm; Stage of Change category as *Precontemplation* (no plans to quit), *Action* (actively trying to quit), or *Maintenance* (have already quit); self-reported seizures in the past year; untreated cardiovascular disease. Women will be excluded if they self-report breast-feeding or are pregnant (verified by urinalysis).

Justification for Equitable Enrollment of Subjects: No one will be excluded on the basis of gender, race, or ethnicity.

Data/Safety Monitoring: The PI ([name], Ph.D.) will be responsible for executing the Data and Safety Monitoring Plan (DSMP), and complying with all reporting requirements.

Data Security: All data (questionnaires, CO samples, tobacco use behavior) will be treated with professional standards of confidentiality. Data will be identified by code number only and stored on password-protected computers kept within locked rooms. Participants' names are not directly associated with these data. The consent forms will be kept in the office of a PI ([name]), also in a locked cabinet.

Safety Monitoring Plan: In the unlikely event of adverse event(s) during the conduct of the study described in this application, the laboratory has a mechanism in place to ensure that the event(s) will be reported to the IRB in a timely manner. The PI will report events that are unexpected and possibly, probably, or definitely related to study participation a) within 24 hours if they are fatal, life-threatening, or serious, and b) within 10 calendar days if they suggest greater risk of harm to study participant(s) than was previously known or unrecognized.

How data will ensure safety for more than minimal risk: The inclusion/exclusion criteria ensure that we enroll only regular cigarettes smokers who are generally healthy. That is, we will exclude individuals whose breath tests reveal that they are not smokers, and who report severe medical conditions (i.e., untreated cardiovascular disease, seizures). Once enrolled, participants will be given varenicline (an FDA-approved tobacco-cessation pharmacotherapy) for 12 weeks. Participants who experience intolerable side effects from

the pharmacotherapy will have the freedom to stop use and withdraw from the study. For all participants, the health risks of study participation do not exceed those normally incurred in their own environment.

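### The COAT group label mixes time in treatment with prior drug abstinence and is assigned by the clinic, so the exploratory group comparison shows associations with clinic group, not an effect of smoking cessation timing

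*Combined protocol and SAP*

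**What the plan says.** Purpose and Objectives describes the groups as stages of treatment: "Days 1 to 90 (weekly group), Days 91 to 180 (biweekly group"), with the monthly group from day 181. Explain the Scientific Rationale repeats this: "various stages of SUD treatment: Days 1 to 90 (weekly group), Days 91 to 180 (biweekly group").

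Probability of Group Assignment says that participants are "assigned to one of three groups based on duration of illicit-drug abstinence and time in COAT program", and then gives the bands in one unit only: "0 to 90 days abstinent (weekly group), 91 to 180 days abstinent (biweekly group"), with the monthly group again from 181. On who decides, it says: "Groups will be assigned by the COAT program at the Chestnut Ridge Center". All three groups receive the same varenicline regimen.

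The lay summary plans to "compare outcomes based on their clinic group". The closing text of the objectives and the Scientific Rationale both go further and promise "initial evidence for whether smoking cessation timing affects abstinence outcomes for both tobacco and opioid use". Potential Benefits to Science/Society poses the same question for relapse: starting at the beginning of opioid treatment versus after stabilization.

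The SAP (Secondary outcomes) compares the groups by one-way ANOVA on relapse to any drug, smoking abstinence at each assessment, days to a successful quit day and withdrawal ratings. It names no covariate. It calls these analyses exploratory and says that the study lacks power for efficacy.

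**The concern.** The clinic group is the only variable in the plan that carries timing. If it is formed partly on how long a person has already gone without illicit drugs, the groups differ at entry on a history close to one of the outcomes, relapse to any drug. The Scientific Rationale also reports that longer smoking abstinence goes with longer opioid abstinence, so the smoking outcome may be related to the label too. A group difference could then appear with no effect of timing. Under the present wording it would be read as evidence that timing matters.

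A reader of the results would also be unable to tell what the groups had represented, because the document does not say that the two durations are recorded separately.

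**Working it through.** **1. The plan's own figure.** The plan gives no figure for the group comparison. Its one precision statement (Sample size: 80% compliance within ±10%, 60 participants) reproduces: 1.96 × √(0.8 × 0.2 / 60) = 0.101. It concerns a feasibility rate and does not bear on this point.

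**2. The two descriptions side by side.**

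| Section | Unit of the bands | Basis named |
|---|---|---|
| Purpose and Objectives; Scientific Rationale | day of SUD treatment | stage of treatment |
| Probability of Group Assignment | days abstinent | abstinence and time in COAT |

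The cut-points (90 and 180) are the same. For someone abstinent since the day of entry, the two durations are equal and nothing turns on the difference. They separate for anyone who used illicit drugs after entry. For example, a patient on day 120 of COAT who last used 30 days ago falls in the biweekly band by treatment day and the weekly band by days abstinent. The clinic will give this patient one label, but the document does not let a reader work out which.

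**3. Would a clear rule allow a timing conclusion?** Take each definition in turn.

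- *By time in COAT.* The monthly group consists of people who have already stayed in the program for at least 181 days. The weekly group includes people who will soon leave; Sample size expects the greatest dropout there and estimates it at 20%. The groups differ in retention before varenicline starts.
- *By days abstinent.* The monthly group has gone at least 181 days without illicit drugs, and relapse is then an outcome. The groups differ on a history close to that outcome.

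In both cases everyone receives the same regimen, so no stage of treatment has a comparator without varenicline. A difference in relapse between the weekly and monthly groups could be the ordinary course of relapse by stage. With neither randomization nor a covariate in the ANOVA, the comparison cannot separate these explanations from timing.

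**4. The date of the label.** The plan does not state the date at which the group is read. Treatment lasts 12 × 7 = 84 days. A person who enters on day 7 reaches day 7 + 84 = 91 by the end and has crossed the first cut-point. A relapse during the study would also shorten days abstinent. A label read after entry could therefore depend on the outcome.

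**5. Illustration that the definition can matter.** Every parameter here is assumed. Days in COAT are uniform on 1 to 365. A latent stability trait (standard normal, s) sets time since last use as exponential with mean 120·exp(s) days, capped at days in COAT. The log-odds of smoking abstinence are −1 + b·s. There is no timing effect, 20 participants per group, and ANOVA at 0.05, with 1,500 runs per cell.

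| b | Rejections, grouped by days abstinent | Rejections, grouped by time in COAT |
|---|---|---|
| 0 | 4.9% | 5.1% |
| 0.5 | 9.3% | 4.3% |
| 1.0 | 23.3% | 5.6% |

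At b = 1.0, mean smoking abstinence under grouping by days abstinent is 25%, 37% and 46% across the three groups. This shows a mechanism, not its size in this trial. The right-hand column looks clean only because the simulation has no dropout from COAT, so it understates selection under that definition.

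**6. What a table of both durations could show.** One participant is 1/20 = 5% of a group. As hypothetical counts, with exact 95% limits: if the bands agreed in all 60 participants, the upper limit for disagreement would be 1 − 0.025^(1/60) = 6.0%; if 6 of 60 disagreed, the interval would be 3.8% to 20.5%.

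**The case against.** Four arguments on the other side have force.

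- *The sections are compatible.* A reader might infer a flat contradiction between them. The documents do not support that: Probability of Group Assignment names both criteria, and the earlier sections never say that their days count from COAT entry. It can be read as completing them. What stands is that the combination rule is missing.
- *Membership is not ambiguous in operation.* A reader might infer that the study team could choose a participant's group. It cannot, because the COAT program assigns it, and that label is what is analysed. The gap is in what the label measures.
- *Abstinence may belong to timing.* Purpose and Objectives contrasts immediate treatment with treatment "after a delay (to allow patients to stabilize on their SUD pharmacotherapy"). If stabilization is the intended exposure, days abstinent is part of it and not only a confounder. The document does not say. This stands, and it argues against adjusting for abstinence by default.
- *The plan is already modest.* It promises only initial evidence, calls the comparison exploratory and disclaims power for efficacy. This lowers the priority but does not answer the point: low power concerns precision, whereas the difficulty is what a difference would mean.

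The Scientific Rationale should not be pressed too far either. It reports an association between two durations of abstinence, not that abstinence before enrolment predicts later quitting or relapse. That further step is plausible, but it is an inference.

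**Conclusion.** The point holds in a limited form. The group label mixes time in treatment with prior drug abstinence in a way the plan does not describe. The clinic-assigned, unadjusted comparison cannot support a statement that timing affects tobacco or opioid outcomes.

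A reader might infer that the unclear definition is what defeats the timing conclusion, so that a clear one would rescue it. It would not. The limit comes from non-randomized clinic assignment and remains under either definition; the missing rule only makes a difference harder to interpret.

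The size cannot be stated. The documents give no relapse rate, no retention after relapse and no distribution of days in COAT, and nothing shows how many participants' durations would disagree. The conclusion assumes only that prior abstinence or retention is plausibly related to relapse and smoking abstinence.

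Priority is low to moderate. The primary feasibility outcomes are descriptive and do not depend on this comparison.

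**What to change.** 1. Describe the clinic's existing grouping rule once, including how abstinence and time in COAT combine, and use the same description in Purpose and Objectives, the Scientific Rationale and Probability of Group Assignment. Clinic practice need not change.
2. State in the SAP that analyses use the clinic group at enrolment.
3. Record days in COAT and days abstinent on that date from clinic records. Tabulate both by group, with the number of participants whose two durations fall in different bands.
4. Report the ANOVA results as associations with clinic group, not as a timing effect. Reword the two statements on initial evidence and the one in Potential Benefits to match, for example: initial evidence on how outcomes differ between COAT clinic groups.
5. Plan no adjusted estimate by default. If one is added, warn that adjusting for days abstinent may remove part of what timing is meant to be.

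The cost is two data items per participant, one small table and a more modest conclusion. Sample size and treatment are unchanged.

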**Subjects:**

**Participant Identification and Recruitment:** Male and female smokers will be recruited from the Chestnut Ridge Center at WVU. Study enrollment will be open to any person who is enrolled in Comprehensive Opioid Addiction Treatment (COAT) at Chestnut Ridge Center for opioid dependence and is eligible based on screening procedures.

**Protection of WVU employees/students:** WVU employees and students are not specifically targeted. However, these individuals may be included in the study if they are enrolled in COAT at Chestnut Ridge Center and are deemed eligible based on inclusion/exclusion criteria. Of course, they will be assured the same rights and protections as all other participants. Informed consent will be performed by a trained staff member and individuals will be informed of the voluntary nature of their participation. Their protection will be maintained by keeping the consent forms, which contain their full name, separate from all session data. Specifically, consent forms will be kept in the office of the PI in a locked cabinet. Additionally, all computerized data will be stored on password-protected computers that are kept within a locked laboratory.

**Additional Provisions of WVU employees/students:** WVU employees and students will be informed that their participation will in no way affect their status at WVU as an employee or student. Additionally, any participants who are current students of [name] will be assured that their participation will in no way affect their status in her class. As always, they will be able to withdraw from the study at any time without any adverse consequence.

**Consent Process (when, where, and how):** Participants will be individuals enrolled in COAT at Chestnut Ridge Center at WVU. A trained member of our research team will visit Chestnut Ridge Center during regularly scheduled COAT meetings times for the informed consent process. Administration of the consent form will take place in a private room at the Chestnut Ridge Center by a trained staff member or co-investigator.

**Sample size:**

**Justification:** The sample size for this feasibility study is based on the estimated rate of attrition for the weekly group of COAT patients. The weekly group consists of those patients in the earliest stage of treatment, during which dropout rates would be greatest. The estimated dropout rate for this group is 20%. Thus, with 60 participants (n=20/group: weekly, biweekly, and monthly) we would be able to estimate a compliance rate for intervention of 80% within  $\pm 10\%$ .

**Management of information relevant to human subjects protection:** Any unanticipated problems experienced during the course of the study or other interim results will be reported appropriately to the IRB within the approved timeline. Moreover, as needed, interim results will be reported to participants prior to their enrollment into the study. Such interim results include any varenicline side effects that have not been commonly reported in the literature, including those outlined in the consent form (e.g., nausea, vomiting, sleep problems, and abnormal dreams).

**Potential Risks/Discomforts:**

Cigarette smokers who abstain from tobacco (i.e., those who choose to cut down or quit regular cigarettes) may experience an aversive withdrawal syndrome that includes irritability, restlessness, difficulty concentrating, hunger, and craving or urges to smoke. These effects can be uncomfortable but are not medically dangerous. These participants may also experience side effects reported of varenicline use: nausea, vomiting, sleep disturbance, abnormal dreams, gas, constipation. Notable is that these effects have been shown to dissipate with continued varenicline use, and do not appear to be significantly different from that incurred when using other nicotine replacement products like the patch (Bullen et al., 2013).

Participants may also experience some discomfort when the nurse inserts or withdraws the needle, or when blood samples are taken. We try very hard to minimize patient discomfort at these times, and the use of a trained nurse and sterile, disposable equipment enhances comfort while reducing the risk of bruising and infection.

Researcher interaction with participations kept private: Researchers will interact directly with participants in person. Individuals who are enrolled in the COAT program at Chestnut Ridge Center will be described the study requirements via the consent process. At each contact, study staff will be sensitive to collecting only that information that the person voluntarily reveals. Additionally, both the screening and session visits will occur in one of the Chestnut Ridge Center session rooms, which can only be accessed by trained personnel and current patients.

